The implementation steps of the proposed study were as follows: (1) The staff introduced the study to all eligible participants either in person or virtually and consented interested families for the study; (2) All participants and their families completed a baseline study survey in REDcap; (3) All participants were trained to wear a blinded CGM using manufacturer educational materials under the supervision of research staff. Participants be changed the CGM sensor every 14 days for the duration of the study. During each study visit, the CGM reader was connected to the site database to create an individual participant report. All equipment required for the duration of the study was distributed to the participants at consent. Participants received enough sensors to wear the CGM daily for the entire study period. (4) All participants and their families received standard nutritional counseling and were randomized to one of three meal-timing schedules followed for 12 weeks: (1) Control or (2) TLE blinded CGM use, and (3) TLE real-time CGM use. During the eating window, participants were not required to count calories or monitor their food intake. Participants chose and paid for their own food during the intervention. All participants recorded their eating window daily and submitted it to the study staff via REDcap. All participants received standard recommendations for physical activity, screen, and sleep time as per the American Academy of Pediatrics age-appropriate recommendations at the first visit; (5) The study staff conducted study assessments with participants at week 0, 4, and 12; (6) The study staff performed weekly phone encounters with the participants to assess barriers to adherence and eating practices. If a barrier is identified the study staff created a solution plan to promote adherence and retention. The study staff recorded any medication changes or health issues that have occurred in the last 7 days. The PI reviewed CGM downloads collected at each study visit to ensure no treatment escalation is required; (7) To further inform future trials and scalability we collected continuously recruitment, consent, and retention rates, and barriers to engagement; (8) Adverse events were monitored. If at any time, the study staff noticed any unhealthy compensatory behaviors the PI was notified, and a treatment plan was created to ensure that the participant receive the appropriate screening, work-up, and diagnosis from their primary care provider and are withdrawn from the study if appropriate. (9) The PI and research team meet bi-weekly to monitor all study procedures and oversee data management and analysis.

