
Participants: We recruited 50 adolescents (age 14-18 years at enrollment, all gender expressions), with obesity. Inclusion criteria are: (1) age 14-18 years; (2) Tanner stage III and above; (3) obesity; (4) hemoglobin A1c ≤ 5.7%; (5) participant must be willing and able to adhere to the assessments, visit schedules, and eating/fasting periods; and (6) baseline eating window greater than 10 hours. To limit confounding factors, individuals will be considered ineligible to participate if they meet any of the following exclusion criteria: (1) diagnosis of Prader-Willi Syndrome, brain tumor or hypothalamic obesity; (2) serious intellectual disability; (3) previous diagnosis or subthreshold symptoms of an eating disorder (anorexia nervosa, bulimia nervosa, binge-eating disorder); (4) parent/guardian-reported physical, mental or other inability to participate in the assessments; (5) previous

bariatric surgery; (6) current use of an anti-obesity or other diabetes medication (e.g., phentermine, topiramate, orlistat, glucagon-like-peptide-1 agonist, naltrexone, bupropion, SGLT-2 Inhibitor, or insulin); or (7) current participation in other interventional weight loss studies. A random block stratified randomization scheme was used. Participants were randomized 1:1 via stratified, blocked randomization to ensure the groups were balanced in terms of number of participants and distribution of potential confounding variables including sex and age.

Retention strategies. To foster treatment adherence, participants received weekly calls from the study staff for the duration of the trial. Counseling was conducted by trained research staff. The sessions served three purposes: (1) foster adherence, retention, and accountability; (2) troubleshoot intervention barriers; and (3) monitor safety endpoints. To support participants, the staff will use behavioral techniques, such as stimulus control, goal setting, behavioral contracting, and motivational interviewing. In order to reduce participant burden, if at all possible study procedures will be scheduled to coincide with participants' scheduled clinical visits.

Intervention Arms:

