The study was a pilot trial, thus we opted for a convenient sample size of 50 participants to estimate parameters for a larger, fully powered trial. Analyses were based on the intention to treat (ITT) population using the last observation carried forward. The ITT population was defined as at least two visits (baseline and 1 month). The study was designed as a three-group intervention analysis; however, given that very few adolescents in the TLE+ real-time CGM feedback group looked at their real-time data, we completed a post hoc analysis combining both TLE groups compared to control for all analyses performed. Baseline characteristics (age, sex, race, BMI status, household income) were summarized descriptively across arms for the ITT population using mean and standard deviation (SD) or median and interquartile range as appropriate for the distribution of continuous variables. Categorical variables are described as a frequency and percentage. Continuous variables that are skewed were analyzed in log scale. The differences in demographics, anthropometrics baseline, and eating window distributions among intervention groups were examined using analysis of variance (ANOVA) and Fisher's Exact test. Adherence was operationalized as the number of days adolescents complied with their prescribed eating window, number of days they wore their CGM, and number of weekly phone calls and scheduled research visits they attended, and satisfaction scores were summarized using mean, standard deviation (SD), minimum, and maximum score between TLE and control. The TLE effect on mean change of %BMIp95 between week 0 and week 12 was assessed by using ANOVA. Then, a mixed-effects generalized linear model based on a Gaussian or Gamma distribution as appropriate was used to further assess the TLE effect on change in weight outcome from week 0 to week 12. The mixed-effects generalized linear model based on a Gaussian or Gamma distribution was used as appropriate for the distribution of continuous outcome variables. Whereas a mixed-effects logistic regression model was used for binary clinical outcome variables. In addition, a mixed effects Tobit regression model was used to evaluate the TLE effect on the change in quality- of-life assessment, where the scores are reported in percentages, with no data below 0 or above 100. Then, the non-additive effects of TLE were also examined; specifically, whether the change on clinical outcomes during the study period varied by intervention groups by including the interaction term in the mixed-effect models. In addition, sensitivity analysis was performed to examine whether the weight change observed in the data was influenced by one adolescent who achieved a weight loss of greater than 15% from baseline weight. All results are described in beta estimate, β , percent change, and odds ratio with its associated 95% confidence interval and p-value. The statistical

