
significance level was set at 0.05 with two-sided throughout the analyses. All statistical computations were done in Stata/SE 17.0 (StataCorp, College Station, TX, USA).

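### The stated 1:1 allocation does not describe three arms; if the arms are equal in size, the pooled TLE v control contrast is about 33 v 17, where the equal-variance ANOVA of %BMIp95 change could misstate its error if group SDs differ.

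*Combined protocol and SAP*

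**What the plan says.** **Allocation.** The Participants section reads: "Participants were randomized 1:1 via stratified, blocked randomization to ensure the groups were balanced in terms of number of participants".

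**Number of arms.** Step (4) of the implementation steps says that participants "were randomized to one of three meal-timing schedules followed for 12 weeks": control, TLE with blinded CGM, and TLE with real-time CGM. The Statistical Analysis section agrees: "The study was designed as a three-group intervention analysis". No arm sizes are given.

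**What is compared.** The same section then says "we completed a post hoc analysis combining both TLE groups compared to control for all analyses performed".

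**How it is tested.** "The TLE effect on mean change of %BMIp95 between week 0 and week 12 was assessed by using ANOVA". A mixed-effects generalized linear model, Gaussian or Gamma, follows for the weight outcome. Skewed variables are analysed on the log scale, and a sensitivity analysis examines one adolescent who lost more than 15% of baseline weight. The "significance level was set at 0.05 with two-sided throughout the analyses". No variance check, unequal-variance test or robust standard error is mentioned.

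**Status.** Anthropometrics come under the Secondary Outcome heading; the SAP's primary outcome is feasibility. On size, "we opted for a convenient sample size of 50 participants to estimate parameters for a larger, fully powered trial".

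**The concern.** A two-part ratio cannot describe three arms, so the reader does not know how many participants stand on each side of the contrast that is reported. If the arms are equal in number, as the Participants section intends, pooling two of them produces a 2:1 contrast, which the plan does not mention.

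This matters because a two-group ANOVA is the pooled-variance t-test. With equal group sizes, that test is nearly immune to unequal variances. At 2:1 it is not. The pooled variance is weighted towards the larger group, so the standard error is too large if the larger group is the more variable one, and too small if the smaller group is. At stake are the confidence interval and p-value for the change in %BMIp95. So is the usefulness of the pilot's variance estimates for the larger trial, since a single pooled SD would conceal any difference between groups.

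**Working it through.** **Inputs.** From the documents: N = 50; three arms; both TLE arms pooled against control; ANOVA; two-sided 0.05. Assumed: equal arms, normal outcomes, and SD ratios from 1 to 2. The sample size is one of convenience, so there is no design calculation to reproduce.

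**Group sizes.** 50 × 2/3 = 33.3 and 50 × 1/3 = 16.7, so about 33 v 17.

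**Standard errors.** With nT = 33, nC = 17 and the smaller SD set to 1:

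- pooled variance = (32 × sT² + 16 × sC²) / 48
- SE used by ANOVA = √[pooled variance × (1/33 + 1/17)]
- true SE = √(sT²/33 + sC²/17)

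Example with the TLE SD twice control: pooled variance = (32 × 4 + 16 × 1)/48 = 3.0; ANOVA SE = √(3.0 × 0.0891) = 0.517; true SE = √(4/33 + 1/17) = 0.424; ratio 1.22, so the SE is 22% too large. Reversed: pooled variance = (32 × 1 + 16 × 4)/48 = 2.0; ANOVA SE = 0.422; true SE = 0.515; ratio 0.82, so the SE is 18% too small.

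**Type I error at nominal 5%.** Simulated under the null with 2,000,000 normal trials per row; separate runs with fewer trials agree to about 0.1 percentage point.

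| SD, TLE : control | ANOVA SE / true SE | ANOVA type I error | Welch type I error |
|---|---|---|---|
| 1 : 1 | 1.00 | 5.0% | 5.0% |
| 1.25 : 1 | 1.07 | 3.6% | 5.0% |
| 1.5 : 1 | 1.13 | 2.7% | 5.0% |
| 2 : 1 | 1.22 | 1.9% | 5.0% |
| 1 : 1.25 | 0.93 | 6.8% | 5.0% |
| 1 : 1.5 | 0.88 | 8.4% | 5.0% |
| 1 : 2 | 0.82 | 10.9% | 5.0% |

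**Other group sizes.**

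- At 25 v 25 the SE ratio is 1.00 throughout, and ANOVA stays at 5.0% to 5.2%.
- At 34 v 16, or at 30 v 15 and 27 v 13 after attrition, the distortion is similar or slightly larger: 1.6% to 1.8% with TLE SD doubled, 11.2% to 11.9% with control SD doubled. Attrition is relevant because the ITT population requires the 1-month visit.
- The three-arm F-test at 17/17/16 gave 5.1% to 6.6% for the unequal-SD patterns tried, so most of the exposure comes from pooling.

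**How much could pooling itself widen the TLE group?** If the two TLE arms have SD 1 and means d apart, the pooled SD is √(1 + d²/4). For d = 0.5 this is 1.03, a 3% increase.

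**Limit of Welch.** With strongly skewed (exponential) outcomes at 33 v 17 and control wider by 1.25 to 2 times, Welch gives about 6.0% to 7.3% and the pooled test about 6.5% to 11.7%. Welch does better but does not hold 5%.

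**The case against.** The strongest reply is that the harm is hypothetical. The documents state neither arm sizes nor SDs. With equal SDs the 2:1 split does no harm to the error rate, and at a ratio of 1.25 the effect is modest. If 1:1 meant control against all TLE participants, the split would be 25 v 25 and the problem would nearly vanish. All of this stands, which is why the point is conditional. It does not remove the need to state the ratio and arm sizes, because only those can settle which case applies.

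Four stronger readings are tempting, and the documents do not support them:

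- **That unequal spread is likely and inflates false positives.** The features that make unequal spread plausible, namely two TLE regimens in one group and uneven adherence to a restricted window, would mainly widen the TLE group. That makes ANOVA conservative: power is lost, but false positives are not created. Nothing in the documents suggests that control is the wider group. The arm of the adolescent with more than 15% weight loss is not stated, so that case supports neither direction.
- **That ANOVA is the only efficacy test.** Mixed models follow it directly. They soften the point without removing it: a Gaussian mixed model with default residuals also assumes equal variance, and the Gamma and log-scale options relax that only in part.
- **That the 2:1 split costs precision.** The SE at 33 v 17 is 5.6% larger than at 25 v 25, since √(1/33 + 1/17)/√(2/25) = 1.056, but three equal arms would never give 25 v 25. Against a single pairwise contrast of 17 v 17, it is 13% smaller: 0.2985/0.3430 = 0.87.
- **That Welch is a complete cure.** It holds 5% for normal data, not under strong skew.

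It is also fair to say that this is a pilot with feasibility as its SAP primary outcome, and that the data-driven decision to pool is a separate and larger matter. Both limit the weight of this point.

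**Conclusion.** The conflict between a 1:1 ratio and three arms is on the page and needs no assumption. The statistical consequence is conditional. It requires three arms of roughly equal size, giving about 33 v 17, and group SDs that differ. Under those conditions the ANOVA's type I error runs from about 1.9% (TLE SD twice control) to about 10.9% (control SD twice TLE). It is 3.6% or 6.8% at a ratio of 1.25, and 5% with equal SDs. The more plausible direction is the conservative one. The documents do not show that the reported interval or p-value is wrong, only that the method is exposed to an assumption that the plan neither checks nor needs. This is a worthwhile, low-cost improvement to a secondary analysis and does not threaten the trial's main purpose.

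**What to change.** 1. In the Participants section, replace the 1:1 statement with the ratio actually used (1:1:1 if the three arms were equal). Give the number randomized and the number analysed in each arm, and state the resulting split of the pooled contrast.
2. Report the SD of the week 0 to 12 change in %BMIp95 by group, ideally for each of the three arms. The larger trial will need these figures.
3. Test that same change with Welch's test, or with HC3 standard errors in a regression on group. The outcome stays as planned.
4. In the Gaussian mixed model that follows, use robust standard errors or a group-specific residual variance.
5. Keep the planned sensitivity analysis for the participant with large weight loss, since Welch does not fully protect against strong skew, and state that participant's arm.

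The cost is one corrected sentence, a few reported figures and one estimation option. If the variances are in fact equal at 33 v 17, Welch's degrees of freedom fall from 48 to about 32: (1/33 + 1/17)² / [(1/33)²/32 + (1/17)²/16] = 32.4. The critical value then rises from 2.01 to 2.04, an interval about 1% wider.

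### The weight effect is tested by an unadjusted ANOVA of change in %BMIp95, and no model names the baseline value as a covariate: valid, but a near-free adjustment is forgone (low severity)

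*Combined protocol and SAP*

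**What the plan says.** All of this is in the Statistical Analysis section unless noted.

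- **Weight test.** "The TLE effect on mean change of %BMIp95 between week 0 and week 12 was assessed by using ANOVA". No covariate is given.
- **Follow-on model.** A mixed-effects generalized linear model, Gaussian or Gamma, "was used to further assess the TLE effect on change in weight outcome from week 0 to week 12". Logistic and Tobit mixed models are named for binary and quality-of-life outcomes. No covariate list is given for any of them.
- **Interaction.** The models also examine "whether the change on clinical outcomes during the study period varied by intervention groups by including the interaction term in the mixed-effect models".
- **Baseline.** The only between-group use of baseline that is described is a comparison: "The differences in demographics, anthropometrics baseline, and eating window distributions among intervention groups were examined using analysis of variance (ANOVA) and Fisher's Exact test". No adjustment is tied to it.
- **Randomisation** (Participants paragraph). It is stratified and blocked to balance the "distribution of potential confounding variables including sex and age". Baseline %BMIp95 is not named as a factor.
- **Purpose and size.** "we opted for a convenient sample size of 50 participants to estimate parameters for a larger, fully powered trial". The "significance level was set at 0.05 with two-sided throughout the analyses".

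The SAP's primary outcome is feasibility. Anthropometrics come under Secondary Outcome.

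**The concern.** A change score assumes that a participant who starts one unit higher is expected to end one unit higher. If the true slope is below 1, the arm that happens to start higher shows a larger fall through regression to the mean, and part of that fall is counted as treatment effect. In a trial of 50, chance differences between arms at baseline are not small, and baseline %BMIp95 is not a named stratification factor. ANCOVA estimates the slope from week-0 data that the trial already collects.

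Two things are at stake: the width of the intervals, and the variance estimate handed to the next trial. A pilot run to supply parameters for a larger study should report the baseline-adjusted residual SD, and the plan does not provide for it.

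**Working it through.** **The plan's own figure.** The only design figure is N = 50. It is a convenience sample with no effect size, SD or power, so there is nothing to reproduce.

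**Inputs.** From the documents: N = 50, two-sided 5%, both TLE groups pooled against control. Assumed, because the documents do not give them: r; k = SD(week 12)/SD(week 0); and arm sizes of 33 and 17. The text says 1:1 but describes three groups, so 25:25 was run as well.

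**Formulas** (linear Gaussian model, baseline SD = 1):

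- Variance of change is proportional to 1 + k² − 2rk. Residual variance under ANCOVA is proportional to k²(1 − r²).
- At k = 1 the variance ratio, ANCOVA to change score, is (1 − r²)/(2 − 2r) = (1 + r)/2.
- Given the observed baseline imbalance, the change contrast is shifted by (rk − 1) × imbalance, which is (r − 1) × imbalance at k = 1.
- The SD of the chance imbalance is √(1/33 + 1/17) = 0.30 baseline SD (0.28 at 25:25).

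**Interval width.** Simulation of 20,000 trials per setting at 33:17 and k = 1, with t-based intervals so that the lost degree of freedom is counted:

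| r | Large-sample SE ratio √((1+r)/2) | Mean CI width, change | Mean CI width, ANCOVA | Width ratio |
|---|---|---|---|---|
| 0.5 | 0.866 | 1.194 | 1.046 | 0.876 |
| 0.7 | 0.922 | 0.925 | 0.862 | 0.932 |
| 0.8 | 0.949 | 0.756 | 0.725 | 0.960 |
| 0.9 | 0.975 | 0.534 | 0.526 | 0.986 |
| 0.95 | 0.987 | 0.378 | 0.377 | 0.998 |
| 0.97 | – | 0.292 | 0.293 | 1.003 |
| 0.99 | 0.997 | 0.169 | 0.170 | 1.009 |

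Widths are in baseline SDs. At 25:25 the ratios agree to within 0.001. The covariate costs about 1% of width at this size (0.876/0.866 = 1.01), so the gain disappears between r = 0.95 and 0.97.

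**Unequal SDs** (33:17; r = 0.90, 0.95, 0.98). At k = 0.9 the ratios are 0.910, 0.899 and 0.844. At k = 1.1 they are 1.011, 1.003 and 0.953.

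**Remainder from a 1-SD chance imbalance** (k = 1). At r = 0.5: 0.50 × 0.30 = 0.15 baseline SD. At r = 0.9: 0.10 × 0.30 = 0.03. At r = 0.95: 0.05 × 0.30 = 0.015.

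**Mixed models.** If week 0 is one of the repeated responses in a linear mixed model, and the arms are free to differ at week 0, the arm-by-time term with complete data is the difference in mean change. It is then the same unadjusted contrast. If the response is the change itself, the same holds unless week 0 is a covariate. The text does not say which applies.

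**The case against.** Several points against the concern stand.

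- A reader might infer that the mixed models leave baseline out. The text does not say so. It lists no covariates at all (not baseline, sex, age or visit), so the supported statement is that the handling of baseline is unstated.
- A reader might infer that chance imbalance passes whole into the weight contrast, or that the test is biased. It does not, and it is not. The change score subtracts the imbalance, and the remainder averages zero over randomisations. It matters only conditionally, for the one allocation that was realised.
- A reader might infer that the %BMIp95 interval is wider than it need be. If r is about 0.95 or more and the SDs are similar, it is not: the width ratio is 0.998 at 0.95 and slightly above 1 beyond that. A clear gain for %BMIp95 in that range of r needs the SD to change between visits, and the documents give no figure for this.
- The larger gains belong to other outcomes, for which the documents give no r either. The (1 + r)/2 formula and the identity with a difference in change are for linear Gaussian models. Quality of life is analysed by Tobit and other outcomes may use Gamma or logistic models, where these ratios do not apply directly.
- The text was written with data in hand. The same section reports the low use of real-time data that led to post hoc pooling, and a sensitivity analysis around one participant with a large weight loss. Swapping the stated weight test now would be one more post hoc choice.

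What these points do not answer is that the stated weight test is explicitly unadjusted, that no model names baseline, and that adjustment costs at most about 1% of width in the settings examined.

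**Conclusion.** The point holds as one of efficiency and reporting, at low severity. The ANOVA of change is valid under randomisation. It leaves a conditional remainder of (r − 1) × imbalance that ANCOVA would remove.

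For Gaussian outcomes with r between 0.5 and 0.8 and equal SDs, adjustment would narrow intervals by about 12% down to 4%. For %BMIp95 with r near 0.95, the effect on width is about nil. These figures rest on assumed values of r and k and on a 33:17 split. The width ratios barely depend on the split.

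The documents do not support calling the weight test invalid, or saying that baseline was excluded from the mixed models. The stronger reason to act is the pilot's stated purpose: an adjusted residual SD is a useful input to the next trial's sample size, and the plan does not produce it.

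**What to change.** 1. Add an ANCOVA of week-12 %BMIp95 on arm and week-0 %BMIp95. Because the SAP text was written after data were seen, label it post hoc and keep the change-score ANOVA alongside it.
2. In the mixed models for continuous outcomes, either use post-baseline visits as the response with the week-0 value as a covariate, or keep week 0 as a response and constrain the arms to a common week-0 mean. List each model's covariates, and say whether sex and age are among them.
3. Report the adjusted difference with its 95% CI and the residual SD.

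Cost: wording, one model term and one degree of freedom. No new data are needed. The downside is intervals up to about 1% wider when r is very high.

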Title: Time Limited Eating in Adolescents (Time LEAd): a Pilot Study

NCT Number: NCT03954223

Date of Document: 2/6/2023

Version: 7

PI: [name]

Center for Diabetes, Endocrinology, and Metabolism

Children's Hospital Los Angeles

Los Angeles, CA 90027

Overview of Study Design from Study Protocol:

The aim of this study will be to compare cardiometabolic effects of TLE (8-h eating period/16-h of daily fasting) versus a prolonged eating period (12+ h eating period) in a randomized pilot study with careful control of continuous adherence to prescribed eating window. This study was a prospective, randomized controlled pilot study in 50 adolescents (ages 14–18) with obesity (BMI% ≥ 95th percentile) recruited from clinical programs at Children's Hospital Los Angeles (CHLA). Patients will be randomized to one of three treatment groups for a 12-week intervention: Group 1): Control - Low sugar and carbohydrate educational intervention (LSC, < 5% of total daily calories from sugar/day; < 90 g carbohydrate (CHO)/day) + blinded CGM (used to monitor adherence and glycemic outcomes without real time feedback). Group 2): LSC + TLE (16-h fast/8-h feed for 5 days per week) + blinded CGM.

Table 3: Study Procedures and Measures

Weeks	0	4	12
Consent Completed	x		
Medical history	x		
Demographic Data	x		
CGM Education and equipment	x		
CGM (sensor change every 14 d, 12 w wear time)	x	x	x
Randomized	x		
Primary Outcomes			
Glycemic Control			
Percent Time in Range	x	x	x
Hemoglobin A1c	x	x	
Secondary Outcomes			
Nutrient Data System Recall: 24-hour dietary recall	x	x	
International Physical Activity Questionnaire	x	x	x
Pittsburg Sleep Quality Index and Chronotype Questionnaire	x	x	x
Monitoring for Adverse Events			
Dutch Eating Behavior Questionnaire	x	x	x
Binge Eating Disorder Screen	x	x	x

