Adherence Monitoring and Intervention Fidelity: To ensure differentiation between the intervention arms all participants recorded the time they start, and finish eating each day and provide their eating logs to the study staff weekly. Each week, study staff will determine the daily eating window for each participant by reviewing the time interval between the first and last caloric intake of the day. These self-reported time windows will be verified by examining the pattern of glucose excursions using the 24-h CGM data. If a participant adheres to meal timing protocol \leq 4 days/week, a follow-up call or videoconference will be scheduled to address challenges, give participants additional encouragement, support, and create a specific plan to promote adherence.

Continuous Glucose Monitor. All participants will be trained to wear a blinded continuous glucose monitor sensor using manufacturer educational materials under the supervision of research staff. Participants will be asked to wear the CGM for the duration of the study. During each study visit, the CGM reader will be connected to the site database to create an individual participant report. Participants will be provided enough sensors to replace the sensor every 14 days. The participants and guardians will be educated on how to use the CGM and receive 1:1 coaching on how to change the sensor, which will be completed either independently or under study team guidance. At each weekly phone meeting, study staff will monitor any challenges related to CGM wear, including participant discomfort, skin adherence, and other issues.

Measurements: The study team will conduct all assessments at week 0, 4, and 12. All data was collected and stored in REDCap.

Statistical Analysis Plan:

Primary Outcome—Feasibility

Compliance with the recommended eating windows was collected from adolescents during the weekly phone calls with the study team. Adolescents were asked to record the time they started and finished eating daily, the number of days they adhered to their prescribed eating schedule, and barriers to adherence. Adolescents were instructed to wear their CGM daily for the duration of the study and to report deviation from the protocol during the phone calls.

Secondary Outcome

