Anthropometrics. All participants received a wireless Bluetooth scale upon consent. Participants' height and weight were collected by the participant and parent/guardian at home with the research coordinator monitoring the measurement collection via a HIPAA compliant virtual platform. Height was measured using a portable wall height indicator tape ruler, accurate to 0.5 cm (Posh Rulers, Quick Medical, Issaquah, WA). Weight was measured on a self-calibrating Etekcity Digital Body Weight Scale, accurate to 0.2 kg (Etekcity, San Diego, CA). Adolescents wore minimal clothing during the height and weight measurements. BMI was calculated as kilograms per meter squared excess percent of the 95th percentile (%BMIp95) was determined utilizing the CDC growth charts.

Continuous Glucose Monitoring

CGM data were downloaded weekly by the study team. CGM data were evaluated continuously over the study period. This data was utilized to compute the following measures: mean, maximum, and minimum glucose levels; standard deviation of glucose; mean amplitude of glycemic excursion; and overall percent of total time spent in euglycemic range (percent time in range = 70–180 mg/dL). All CGM data were housed in Clarity (Dexcom and Dexcom CLARITY are registered trademarks of Dexcom, Inc., San Diego, CA, USA) and the study team had weekly access to assess all glycemic excursions that occurred during the self-reported fasting periods [50–53]. For those in the TLE + real-time

Statistical Analysis

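### A pilot sized for estimation judges every comparison at 0.05 with no exploratory label, and plans no interval for its feasibility rates or outcome variability

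*Combined protocol and SAP*

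**What the plan says.** **Purpose.** Under Statistical Analysis the authors write that "we opted for a convenient sample size of 50 participants to estimate parameters for a larger, fully powered trial". No effect size, SD or power is given. The SAP opens with the heading "Primary Outcome—Feasibility", covering eating-window compliance and CGM wear.

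**Inference rule.** The same section ends by stating that the "significance level was set at 0.05 with two-sided throughout the analyses". It contains no multiplicity adjustment, no hierarchy and no exploratory label. It describes the study as a pilot and the pooling of the two TLE arms as post hoc.

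**Weight/BMI.** The week 0 to week 12 change in %BMIp95 is tested by ANOVA. A mixed-effects generalized linear model then "was used to further assess the TLE effect on change in weight outcome from week 0 to week 12". An interaction term and a sensitivity analysis for one participant with large weight loss follow. No sentence says which result is the reported one.

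**Intervals.** All model results (beta, percent change, odds ratio) are to be given with a 95% confidence interval and a p-value. Adherence, CGM wear, attendance and satisfaction are summarised by mean, SD, minimum and maximum only. Step (7) of the implementation steps says that, to inform future trials, "we collected continuously recruitment, consent, and retention rates, and barriers to engagement"; the SAP gives these rates no analysis.

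**The concern.** The design asks for estimation, but the reporting rule is the one used for confirmatory testing. With many outcomes read against 0.05 and none marked as the one that counts, a chance finding could be carried into the larger trial as evidence that TLE works. The documents do not even settle which comparison would be protected: Table 3 places percent time in range and "Hemoglobin A1c" under primary outcomes, while the SAP names feasibility.

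Meanwhile the quantities that justified recruiting 50 people are only partly provided for. A larger trial needs the consent rate, retention, adherence, the SD of the outcome and its correlation with baseline, each with its uncertainty. The plan collects or could compute all of them, but commits to an interval for none.

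Two analyses of the 12-week weight effect with no stated priority leave open which is reported as the result.

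**Working it through.** **Is there a figure to reproduce?** No. The 50 is a convenience sample without inputs. The only stated error rate is two-sided 0.05.

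**Step 1: count the outcomes.** The SAP names TLE tests for %BMIp95, weight and quality of life, and covers the rest with general model sentences. The count below is therefore inferred from what is measured.

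| Source | Outcomes | Number |
|---|---|---|
| Continuous Glucose Monitoring section | "mean, maximum, and minimum glucose levels; standard deviation of glucose; mean amplitude of glycemic excursion" (5), plus "overall percent of total time spent in euglycemic range" (1) | 6 |
| Table 3 | HbA1c, dietary recall, physical activity, sleep, chronotype | 5 |
| Table 3, under adverse-event monitoring | Dutch Eating Behavior Questionnaire, binge eating screen | 2 |
| Statistical Analysis | %BMIp95, quality of life | 2 |
| **Total** | | **15** |

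Without the two adverse-event instruments the total is 13. With weight counted apart from %BMIp95 it is 16.

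**Step 2: chance of at least one p<0.05 with no true effect.** If independent, this is 1 − 0.95^k:
- k = 13: 1 − 0.513 = 49%
- k = 15: 1 − 0.463 = 54%, with 15 × 0.05 = 0.75 false positives expected
- k = 16: 1 − 0.440 = 56%

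The outcomes are related, so 15 equicorrelated normal test statistics were also simulated (200,000 draws). The correlations are assumptions, because the documents give none.
- correlation 0.3: 46%
- correlation 0.5: 36%
- correlation 0.8: 20%

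**Step 3: what the second weight analysis adds.** Only weight/BMI is documented as analysed by both ANOVA and a mixed model. Adding one further test, correlated 0.9 (assumed) with the first, to the 15 gives 55%, 47% and 37% at cross-outcome correlations of 0, 0.3 and 0.5. That is about one percentage point more. The double analysis matters as a choice of what to report, and hardly affects the error rate.

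**Step 4: which planning parameters have an interval?**

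| Parameter | Planned summary | Interval planned? |
|---|---|---|
| Treatment effect | Model estimate | Yes, 95% CI |
| Adherence, CGM wear | Mean, SD, minimum, maximum | No |
| Consent and retention rates | Collected; no analysis stated | No |
| SD of week-12 change | Not named | No |
| Baseline to week-12 correlation | Not named | No |

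**Step 5: why the interval matters at this size.** Assume, for illustration only, that 40 of 50 are retained.
- Retention is 80%, with an exact (Clopper-Pearson) 95% CI of 66% to 90%.
- The pooled SD of change from 40 observed participants in two groups has 40 − 2 = 38 df. The limits are SD × √(38/χ²), with χ² quantiles 56.90 and 22.88: √(38/56.90) = 0.82 and √(38/22.88) = 1.29.
- Required sample size scales with SD², so it is uncertain from 38/56.90 = 0.67 to 38/22.88 = 1.66 times the planned figure.

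**Step 6: would a formal adjustment help?** Bonferroni over 15 tests gives 0.05/15 = 0.0033 per test. Arm sizes are not stated. For splits from 16 v 34 to 25 v 25, power for a 0.5 SD effect (two-sample t-test, all 50 analysed) is about 37% to 41% at 0.05, and about 9% to 11% at 0.0033.

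**The case against.** The strongest reply is that this is openly a pilot. The title says so, the SAP makes feasibility primary, the pooled comparison is called post hoc, and no decision about a later trial is tied to p<0.05. Pilots are not normally asked to adjust for multiplicity, and Step 6 shows that adjustment would leave almost no power. This stands as an argument against a formal correction, and none is proposed. It does not supply the missing statement: calling a study a pilot does not tell a reader how to treat a p-value below a level that the plan sets for all its analyses.

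Four stronger readings are tempting, and the documents do not support them.
- A reader might infer that no planning parameter gets an interval. The treatment effect is one, and the plan gives every model effect a 95% CI. The gap is in the feasibility rates, adherence and variability.
- A reader might take the 15 outcomes as the plan's own list. It is an inference from what is measured, and two of the instruments sit under adverse-event monitoring.
- A reader might double the count to 30 on the view that each outcome is tested twice. Only weight/BMI is documented that way.
- A reader might count the interaction terms as a further family of tests. The SAP describes them as asking whether change differed by group. In a longitudinal model that is ordinarily the treatment effect itself.

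**Conclusion.** The point holds in a limited form. The plan's blanket 0.05 rule, without an exploratory label or hierarchy, does not fit a study sized for estimation with feasibility as primary. Under the stated rule the chance of at least one false positive is roughly 36% to 54%, assuming about 15 outcomes and correlations between 0.5 and 0. It would be lower, about 20%, if the outcomes were correlated as strongly as 0.8. The plan also commits to no interval for consent, retention, adherence, CGM wear, the SD of the week-12 change or the baseline to week-12 correlation, and sets no priority between the two weight analyses.

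A reader might go further and conclude that the 0.05 level must be deleted. That is a preference: a clear statement of what the p-values cannot support is enough. Nothing here shows that any reported effect is false.

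**What to change.** 1. State in the SAP that all between-group clinical comparisons are exploratory and that no efficacy claim rests on p<0.05. Lead with the estimates and the 95% CIs already planned.
2. Designate the week-12 %BMIp95 contrast from one named model as the reported weight result, and the other analysis as sensitivity. Label this a post-data choice, because the Statistical Analysis section was written after results had been seen: it refers to one participant's observed weight loss and to how few in the real-time group looked at their data.
3. Add one table with 95% CIs for the consent rate, week-12 retention among all randomised, adherence to the eating window and CGM wear, the SD of the week-12 change, and the baseline to week-12 correlation. Compute the last two from observed week-12 values. The planned last-observation-carried-forward values would mix shorter-term change into the SD, and would make its degrees of freedom look larger than the data support.

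The cost is SAP wording and one table from data already collected, with no new visits or participants. The downside is that nominally significant results cannot be presented as evidence of effect, and that the choice of weight model can no longer be called pre-specified.
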